### 6.6 DOSE DELAYS/MODIFICATIONS

#### 6.6.1 General rules

Dose modifications are permitted according to the guidelines described in this section.

Dose modifications different from those stated in the protocol should only be made in consultation with the Sponsor unless required for immediate patient safety.

Dose adjustment, dose delay (ie, delay of either isatuximab or REGN2810 within a cycle for combination cohorts), cycle delay (ie, delay of both IMPs for combination cohorts, or delay of isatuximab for monotherapy cohorts), or dose omission (ie, omission of either isatuximab or REGN2810 within a cycle for combination cohorts) are permitted in case of toxicity. Dose adjustments will be made according to the worst grade of toxicity observed within a cycle. If a patient experiences several toxicities and there are conflicting recommendations, the most conservative dose adjustment recommended should be followed. Once a dose has been decreased, intra-patient re-escalation back to the previous dose level is not permitted.

Administration of the study treatment will be discontinued in the event of a TEAE that persists despite appropriate dose modifications or any other AE that, in the opinion of the Investigator, warrants discontinuation.

If 1 of the 2 drugs (REGN2810 or isatuximab) is prematurely permanently discontinued, the other drug can be continued until disease progression confirmed by imaging 4 weeks after initial evidence of progression (or 6 weeks for bone progression in mCRPC in Appendix A) as detailed in Section 6.7.1, unacceptable AE, patient's decision, 2 years of uninterrupted delivery of IMP

without documented PD, or administrative reasons. The end of treatment (EOT) assessment in this case will be 30 days after the date of the last IMP administration.

All changes to study treatment administration must be recorded in the electronic case report form (e-CRF).

### 6.6.2 Dose delay and dose omission

Within a cycle, the treatment window is  $\pm 1$  day for each of the weekly administrations and  $\pm 2$  days for each of the Q3W administrations. Within a cycle, a dose is deemed to have been delayed if the treatment is  $\geq 2$  days beyond the theoretical day of treatment for weekly dose, and  $\geq 3$  days beyond the theoretical day of treatment for Q3W dose. The patient will receive the next infusion after recovery of the toxicity as described in Section 6.6.3.

Patients may have dose delay, cycle delay, or dose omission if toxicity occurs and he/she does not recover according to following rules:

- In Cycle 1 (for weekly administration of isatuximab) if toxicity occurs and the patient does not recover on the day of planned infusion or within the following 3 days, infusion of isatuximab (in D8 or D15) may be omitted.
- In Cycle 2 and beyond, if toxicity occurs and the patient does not recover on the day of planned infusion or within the following 14 days, either infusion of isatuximab or REGN2810 may be omitted for combination cohort.
- In case of cycle delay or dose omissions for the recovery of toxicity, the following rules should be followed for restart or discontinue the treatment:
  - In case of a cycle delay up to 14 days or a dose omission, it is per Investigator's decision to restart the study treatment.
  - After a cycle delay of >14 days and ≤84 days, or 2 to 4 consecutive dose omissions, it is per Investigator's decision to restart the study treatment or the IMP that is omitted, if a clear benefit from therapy is observed and after consultation with the Sponsor.
  - The study treatment must be definitely permanently discontinued if the cycle delay is longer than 84 days, or if more than 4 consecutive dose omissions, the IMP will be prematurely discontinued.

#### 6.6.3 Dose modifications

Guidelines for isatuximab and REGN2810 dose modifications and treatment discontinuation due to hematological and non-hematological adverse reactions in general are outlined in Table 2.

See Section 6.6.4 and Appendix G for guidance for irAEs correlated with REGN2810, and Section 6.6.5 for IARs correlated with isatuximab and REGN2810.

The final decision will be based on the Investigator's judgment, in the best interest of the patient.

11-Jun-2019 Version number: 1

Table 2 - Isatuximab and REGN2810 dose modification guidelines

NCI CTCAE V4.03	management	management	Action and Guidelines
Hematological toxicity			
Grade 1, 2, 3	No change		Patient should be given supportive care and monitored closely.
Grade 3 thrombocytopenia asting >7 days or associated with bleeding	Delay the cycle until bleeding is controlled and platelet >50,000/mm³. Restart treatment with same dose and schedule.		Patient should be given supportive care and monitored closely.
Grade 4	Delay the cycle until ANC >1000/mm³, and platelet >50 000/mm³. Restart with same dose and schedule.  Grade 4 lymphopenia: no change in dose		Permanent discontinuation of study treatment should be considered if toxicity does not resolve within 84 days of last infusion.
Febrile neutropenia and/or neutropenic infection	Delay the cycle until fever and infection recover and ANC >1000/mm³. Restart with same dose and schedule.		
Non-hematological toxicity (other than irAE and IAR)			
Grade 1	No change		N/A
Grade 2 (except alopecia) Grade 3	Delay the cycle until improves to Grade ≤1 or baseline.  Restart treatment at same dose and schedule		It is up to the Investigator's judgment whether to restart the treatment of isatuximab and REGN2810 if the cycle delay is within 14 days.
Grade 4	Permanently discontinue treatment for treatment related AEs		
			If the cycle delay is longer than 14 days, before restarting the treatment, the Investigator must discuss with Sponsor; if it is determined that it is to the best interest of the patient, the treatment may be restarted.  If the cycle delay is longer than 84 days, the treatment must be discontinued.
Immune-related AE: see Table 3 and Appendix G for dose modification and patient management guideline			
Infusion-Associated Reaction: see Table 4 for IAR management guideline			

Abbreviations: AE=adverse event; ANC=absolute neutrophil count; DL-1=dose level minus 1; IAR=infusion-associated reaction; irAE=immune-related adverse event.

# 6.6.5 General guidelines for the management of infusion-associated reactions

Patients should routinely receive premedications prior to isatuximab infusion as detailed in Section 8.2 to reduce the risk and severity of IARs commonly observed with monoclonal antibodies.

Infusion-associated reactions (which include NCI-CTCAE, version 4.03 terms "allergic/hypersensitivity reactions" and "cytokine release syndrome/acute infusion reaction")

typically occur within 24 hours from the start of the infusion. If an IAR is observed, patients must also be informed of the potential risk of recurrent allergic reactions at subsequent infusions.

Summary of IAR management is provided in Table 4.

Patients who experience Grade 2 IARs may resume REGN2810/isatuximab infusion after temporary interruption, under close monitoring and with therapy as needed. Patients may receive additional medication per the judgment of the Investigator. Additional recommended medications are: diphenhydramine 25 mg IV (or equivalent) and methylprednisolone 100 mg IV (or equivalent).

Once a Grade 2 IAR has improved or resolved to Grade ≤1, the infusion may be restarted:

- For REGN2810, the infusion should be restarted at half the original infusion rate.
- For isatuximab, the infusion should be restarted at half the original infusion rate, see Section 8.3.1.1 for infusion rate. If symptoms do not recur after 30 minutes, the infusion rate may be increased in 50 mg/hour increments every 30 minutes, to a maximum of 400 mg/hour.

Patients with Grade 3 or 4 IAR must have REGN2810 and/or isatuximab permanently discontinued and appropriate therapy should be administered:

- If a Grade 3 or higher IAR occurs during REGN2810 infusion, REGN2810 should be permanently discontinued. The patient can continue treatment with isatuximab.
- If a Grade 3 or higher IAR occurs after the start of isatuximab infusion, the patient should permanently discontinue treatment with both REGN2810 and isatuximab.

The infusion reaction and the therapy administered must be documented in the case report form (CRF).

Grade 2 or higher IARs must be reported as AESI (see Section 10.5.5). Study personnel should consult the Medical Monitor for further guidance regarding re-treatment of patients with infusion reactions and regarding issues of premedication management (eg, alternative medications for patients allergic or intolerant to premedication agents) or to determine if locally used equivalent medications are acceptable.

Table 4 - Infusion-associated reaction management

Infusion related reaction grading (NCI-CTCAE v4.03 criteria)	Recommendation	
Mild Grade 1 Infusion interruption or intervention not indicated	Continuation of REGN2810/isatuximab infusion is per the judgment of the Investigator following close direct monitoring of the patient's clinical status.  REGN2810/isatuximab infusion may be stopped at any time if deemed necessary. If stopped, IAR will be classified as Grade 2 as per NCI-CTCAE definition.	
Moderate Grade 2 Therapy or infusion interruption indicated but responds promptly to symptomatic treatment (eg, antihistamines, NSAIDS, narcotics, IV fluids); prophylactic medications indicated for ≤24 hours)	Stop REGN2810/isatuximab infusion. Give additional medication(s) with IV diphenhydramine 25 mg (or equivalent) and/ or IV methylprednisolone 100 mg (or equivalent) as needed. REGN2810 a /Isatuximab b may be resumed only after patient recovery, with close monitoring.	
Severe or Life-threatening Grade 3: Prolonged (eg, not rapidly responsive to symptomatic medication and/or brief interruption of infusion); recurrence of symptoms following initial improvement; hospitalization indicated for clinical sequelae  Grade 4: Life-threatening consequences; urgent intervention indicated	Stop REGN2810/isatuximab infusion. Give additional medication(s) with diphenhydramine 25 mg IV (or equivalent) and/ or IV methylprednisolone 100 mg (or equivalent) and/or epinephrine as needed.  If IAR occurred during REGN2810 infusion, permanently discontinue REGN2810. Continue treatment with isatuximab. If IAR occurred after the start of isatuximab infusion, permanently discontinue both REGN2810 and isatuximab.	

a REGN2810: The prepared infusion bag should be kept no more than 8 hours at room temperature, or no more than 24 hours at 5°C (with an acceptable operating range of 2°C to 8°C refrigerator).

Abbreviations: AE=adverse event; CTCAE=common terminology criteria for adverse events; IAR=infusion-associated reaction; IFN=interferon; IL=interleukin; IV=intravenous; NCI=National Cancer Institute; TNF=tumor necrosis factor.

#### 6.7 DURATION OF STUDY PARTICIPATION

#### 6.7.1 Duration of study participation for each patient

The duration of the study for a patient will include a period of screening of up to 28 days, a treatment period (up to 2 years), a safety follow-up period (90 days or until ADA is negative, if ADA test is positive or inconclusive at Day 90), and a survival phone call follow-up period.

**Treatment period**: The cycle duration is 21 days. Patients will continue treatment until disease progression confirmed by imaging 4 weeks after initial evidence of progression (or 6 weeks for bone progression in mCRPC in Appendix A), unacceptable AEs, patient's decision, 2 years of uninterrupted delivery of IMP without documented progressive disease (PD), or administrative reasons.

Patients who have apparent radiographic progression by CT/MRI per RECIST v1.1 or bone scan per PCWG3 criteria are allowed to continue until PD is confirmed providing:

• Absence of clinical symptoms or signs indicating clinically significant disease progression;

b Isatuximab: the infusion should be completed within 16 hours from the end of infusion preparation or a new infusion should be prepared with the remaining dose to be administered the same day.

- No decline in performance status;
- Absence of rapid disease progression or threat to vital organs or critical anatomical sites [eg, CNS metastasis, respiratory failure due to tumor compression, spinal cord compression] requiring urgent alternative medical intervention;
- No significant, unacceptable or irreversible toxicities related to study treatment.

**Safety follow-up period**: After treatment discontinuation, patients will return to the study site 30 days (±7 days) after the last dose of IMP, or when the patient receives another anti-cancer therapy, whichever is earlier, for end-of-treatment assessments. In addition, there will be an extended safety follow-up period for 90 days after the last dose of IMP for ADA assessment and for safety assessment. If ADA test is positive or inconclusive, ADA testing will be repeated every 3 months until negative. All ongoing related AEs, ongoing SAEs and new related AE/SAEs will also be followed up.

Patients who discontinue the study treatment without PD will be followed every 90 days for disease assessment until confirmation of PD or start of treatment with another anti-cancer therapy, or until study cut-off date, whichever comes first

**Survival phone call follow-up period**: The further follow-up schedule beyond 90 days after last dose of IMP is according to the disease progression status:

- Patients who discontinue study treatment due to PD: phone call follow-up will be done every 90 days from the date of last IMP administration until death or study cut-off date.
- Patients who discontinue the study treatment without PD, and without PD confirmed during the safety follow-up period: will be followed every 90 days for disease assessment until confirmation of PD or start of treatment with another anti-cancer therapy, or until study cut-off date, whichever occurs first. After PD patients will be followed by phone call until death or study cut-off date.
- Patients who are still on study treatment after study cut-off date: will continue to receive study treatment and will undergo planned study procedures (except PK and ADA) until confirmation PD, or start with another anti-cancer therapy, or treatment period ended, whichever comes first.

**Cross-over**: The patients in Cohort A-2 treated with isatuximab monotherapy who experience PD will be permitted to cross over to isatuximab in combination with REGN2810 for up to 2 years after progression on isatuximab monotherapy. Safety and efficacy assessments for these patients during the cross-over period are the same as the assessments in the Phase 2 part.

For post OS study cut-off date please refer to Section 12.5.3.

Sponsor has the right to terminate the study at 1 or more sites for any reason.

# 6.7.2 Determination of end of clinical trial (all patients)

The study cut-off is planned at 12 months after the last ongoing patient initiates IMP, or when all participants have had the opportunity to complete the end-of-treatment (EOT) visit 30 days after the last study treatment administration, whichever is the earliest.

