#### Planned date for study cut-off:

The study cut-off is planned at 12 months after the last ongoing patient initiates IMP, or when all participants have had the opportunity to complete the end-of-treatment (EOT) visit 30 days after the last study treatment administration, whichever is the earliest.

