#### 12.5 POST TREATMENT FOLLOW-UP

The post treatment follow-up period includes an extended safety follow-up period of 90 days after the last dose of study treatment and further follow-up beyond 90 days after the last dose of study treatments until death or study cut-off date, whichever occurs first.

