#### 12.5.3 Post overall survival study cut-off date

Patients still on study treatment after the study cut-off date (12 months after last patient initiates IMP) can continue study treatment until at least 1 treatment discontinuation criterion as defined in Section 6.7 is met. The following information will be collected during the study treatment administration:

- IMP administration.
- Disease assessment (for patients who are still on study treatment, until confirmation of PD, or start with another anti-cancer therapy, or treatment period ended, whichever comes first)
- All SAEs regardless of relationship to study treatment and AEs considered related to study treatment.
- End of treatment reason.

One ADA sample should be drawn 90 days after last study treatment administration. If ADA is positive or inconclusive at 90 days, the repeat samples will be taken every 3 months days until the results become negative (see Section 1.5).

No follow-up information will be collected after these patients discontinue study treatment except all SAEs still ongoing at the end of study treatment and all AEs considered as related to study treatment still ongoing or occurring after the end of study treatment, which will be followed until resolution/stabilization.

11-Jun-2019 Version number: 1

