## 13.4.4.1 Analysis of primary efficacy endpoint

The RR will be summarized using descriptive statistics. A 90% 2-sided confidence interval will be computed using Clopper-Pearson method. The statistical inference will be based on the hypothesis defined in Section 13.1 using a 1-sided exact binomial test with a significance level of 0.05 for each cohort. For each cohort, the analysis cut-off date for the primary analysis of RR will be 6 months after the last patient's first treatment in the cohort. The analysis cut-off date for secondary efficacy endpoints including DoR and PFS will be 12 months after the last participant's first treatment in the cohort. The primary analysis of RR will be updated.

Same analysis will be performed for RR using the response evaluable population as a secondary analysis. Subgroup analyses for primary endpoint may be performed if relevant.

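### The study cut-off rule lets follow-up end before the plan's own 12-month DOR/PFS cut-off if every patient comes off treatment early

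*Protocol*

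**What the plan says.** Protocol 6.7.2 gives two conditions. The first is a fixed time: "The study cut-off is planned at 12 months after the last ongoing patient initiates IMP". The second is that all participants have had the chance to attend the end-of-treatment visit "30 days after the last study treatment administration, whichever is the earliest". The synopsis, under the planned date for study cut-off, repeats both conditions and the same operator. The 6.7.2 heading presents this date as the end of the trial for all patients.

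Other places use 12 months with no early branch:

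- Protocol 13.4.4.1 says that the cut-off for "secondary efficacy endpoints including DoR and PFS will be 12 months after the last" participant's first treatment in the cohort. The synopsis (planned date for analysis cut-off) and SAP 2.4.5 agree.
- Protocol 12.5.3 describes the study cut-off as "12 months after last patient initiates IMP".
- SAP 1.5 declares no modification of the protocol's statistical section.

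The study cut-off also ends data collection. Under protocol 6.7.1, the 90-day disease assessments of patients who stopped without progression run no later than study cut-off, and survival calls run to death or study cut-off. Protocol 12.5 describes "further follow-up beyond 90 days after the last dose of study treatments until death or study cut-off date, whichever occurs first".

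**The concern.** The early condition is met when patients leave treatment quickly. If it comes first, scans and survival calls stop then, and no more of those data exist to analyse at month 12. A 12-month analysis could still be run, but on assessments that ended earlier than the plan states. The amendment history (Amendment 3) says that the cut-offs were moved from 6 to 12 months because an early cut-off harms the maturity of DOR and PFS. The early branch can undo that change.

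There is a smaller consequence for safety. SAP 2.1.4 runs the post-treatment adverse-event period from day 31 after the last dose to the protocol-defined end of study. For the last patient to stop, the early branch places that end at day 30.

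**Working it through.** **Dates.** The 12-month figure is a planning date, so there is no power or sample-size figure to reproduce. Count time from the last patient's first dose, and let L be the time of the last dose given to anyone in the study. With 365.25 days in 12 months and 30.4375 days per month:

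study cut-off = min(365.25, L + 30) days.

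The early branch comes first when L < 365.25 − 30 = 335.25 days, or 335.25 / 30.4375 = 11.01 months. It comes before even the 6-month response-rate cut-off when L < 182.6 − 30 = 152.6 days, or 5.01 months.

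| Last dose (month) | Study cut-off (month) | Short of month 12 by |
|---|---|---|
| 4 | 4.99 | 7.01 |
| 6 | 6.99 | 5.01 |
| 8 | 8.99 | 3.01 |
| 10 | 10.99 | 1.01 |
| 12 | 12.00 | 0 |

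**Safety visits.** Protocol 12.5.1 schedules visits at 60 and 90 days after the last dose. When the early branch applies, the last-treated patient's visits fall (L + 60) − (L + 30) = 30 days and (L + 90) − (L + 30) = 60 days after the cut-off.

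**How likely it is.** The documents give neither time on treatment nor accrual duration, so both are assumed: exponential time on treatment with median m months, capped at the protocol's 2 years, and uniform entry over A months. For N patients, approximate the span from start of accrual to last entry by W = A × N/(N + 1), and let u = min(W, 24 − 11.01). Then:

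- q = 2^(−11.01/m) is the chance that the last-entered patient is still on treatment at month 11.01;
- g = q × m/(W ln 2) × (1 − 2^(−u/m)) is the same chance for any other patient;
- P(early branch comes first) ≈ (1 − q)(1 − g)^(N − 1).

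Example with N = 23 + 20 = 43 (Stage 1 of Cohorts A-1 and B), A = 12 and m = 3: W = 11.73, q = 0.0785, g = 0.0270, and P = 0.9215 × (0.9730)^42 = 0.29. Simulation of the same model gives 0.29 to 0.30.

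| N | Accrual (months) | m = 2 | m = 3 | m = 4 | m = 6 |
|---|---|---|---|---|---|
| 43 | 12 | 0.78 | 0.29 | 0.05 | 0.001 |
| 43 | 18 | 0.84 | 0.42 | 0.13 | 0.006 |
| 134 | 18 | 0.61 | 0.08 | 0.003 | <0.001 |
| 134 | 24 | 0.69 | 0.15 | 0.01 | <0.001 |

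The 134 is the planned Phase 2 size, 49 + 49 + 36. Where the branch applies with 43 patients and m of 2 to 4 months, the median cut-off is at about month 7 to 11.

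**The case against.** **The loss is narrow.** The branch applies only when every participant is off treatment; one patient dosed past about month 11 restores the 12-month date. Patients who stopped for progression already have their PFS or DOR event, and those who start new therapy are censored anyway. The DOR/PFS date is per cohort while the study cut-off is study-wide, so mainly the last-enrolling cohort(s) are exposed. All of this stands and limits the size of the point. It does not remove the conflict.

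**The high probabilities are selective.** A reader might infer that early closure is likely. The documents do not support that. The value near 0.8 needs both a study that ends after Stage 1 and a 2-month median, which is 2 × 30.4375 = 60.9 days and so falls before the first scheduled scan at day 63. Cross-over, with up to 2 further years of treatment, would lower the chance again. Stopping after Stage 1 is, however, a possibility that protocol 6.3 provides for.

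**Safety follow-up.** A reader might infer that the last patients lose their Day-60 and Day-90 visits and that late immune-related events go unrecorded. The documents do not say so. The 90-day safety period carries no cut-off clause (6.7.1, 12.5.1), and 12.5 attaches the cut-off only to follow-up beyond 90 days. New related events are followed to resolution or stabilization (12.5.1), and events attributed to the study drug are reportable after the study ends (10.5.3). What remains is that these visits fall after the defined end of trial and outside the SAP window.

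**Overall survival.** A reader might infer that OS misses a stated follow-up. OS is exploratory and has no analysis date of its own, so only the shortening of survival calls can be claimed.

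**Conclusion.** The rule conflicts with the 12-month dates in protocol 12.5.3, protocol 13.4.4.1 and SAP 2.4.5. Followed literally, it can end DOR and PFS follow-up before the stated date. The shortfall is 12 months minus (last dose + 30 days), for example five months if the last dose is at month 6. It affects patients in the last-enrolling cohort(s) who stopped without progression and, for survival follow-up, everyone still alive. The date arithmetic needs no assumption. The likelihood rests on assumed exponential time on treatment and uniform accrual: material with a short median or a study that ends after Stage 1, small at the planned size once the median reaches 3 months or more. The number of patients or events lost cannot be derived from the documents. The wording should be corrected, because follow-up that was not collected cannot be recovered.

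**What to change.** 1. In protocol 6.7.2 and the synopsis, delete the end-of-treatment branch and "whichever is the earliest". State that the study (data) cut-off is 12 months after the last patient's first dose, matching 12.5.3, 13.4.4.1 and SAP 2.4.5. Permit an earlier date only if no patient remains in disease-assessment or survival follow-up.
2. Define the end of trial separately, as not before the last patient's already scheduled Day-90 safety visit, and use that date to close the SAP 2.1.4 post-treatment adverse-event period. Say how this applies to patients still on treatment at the data cut-off, for whom 12.5.3 lists a reduced collection.

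The cost is protocol and SAP wording, plus the already scheduled 90-day assessments and calls between the early date and month 12: five months of them if the last dose is at month 6, none if anyone is dosed past about month 11. No new procedures or patients are needed. The formal end of trial may be later than under the present rule.
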